3.1 BP measurements

All subjects will be asked to measure BP three times a week, twice a day (morning and evening before sleeping). BP will be measured by an automatically oscillometer. The researcher will evaluate the BP each study visit. A mean value of morning and evening measurements will be calculated.

3.2 BIS measurements

Multifrequency BIS measurements will be performed using a commercially available reference device [i.e. Fresenius Medical Care, Body Composition Monitor[®] (BCM)] (Figure 2), and a research device from Imec Eindhoven[®] (Figure 3).

Figure 2 Body composition monitor

Figure 3 Wearable Imec BIS device

Measurements are non-invasive. For every BIS measurement, the patient is asked to lie down in the most comfortable position at around 20/30° supine position with at least 5 minutes of equilibration time before measurements starts. For the reference device, a standardized electrode configuration will be used: two electrodes attached on the foot and two on the hand, ipsilateral. If for one or another reason, it is not possible to attach it on the right side of the body, the left side will be used. No other measurements will be taken simultaneously (i.e. ECG). The applied micro current is alternating between 5 and 1000 kHz.

Next, the wearable research device is attached to the thorax using a total of 9 electrodes, 4 electrodes serve for BIS measurement, 1 bias, 2 for ECG, and 2 other electrodes are necessary to attach the research device to the patient and keep it in a stable position. The five leads are placed in a standardized manner as shown in Figure 4. Each measurement takes 20 minutes.

[figure not shown]

Figure 4 Thoracic electrode configuration of the research device, BIS measurement. I, current; V, voltage

3.3 Cardiac function

At baseline (Visit 0), Visit 2 and Visit 5 of the study, ECG will be performed. At baseline and end of the study, an echocardiography will be planned to evaluate cardiac function. Echocardiography will be performed by professional echocardiographists according to a standardized protocol (in Dutch):

- 1. Parasternale lange as (PLAX)
- 2. Parasternale korte as (PSAX)
- 3. Apicale 4 kamer (A4C) window + idem met nauwe sector width voor offline strain (+ color)
- 4. Apicale 2 kamer (A2C) window + idem met nauwe sector width voor offline strain (+ color)
- 5. Apicale 3 kamer (A3C) window + idem met nauwe sector width voor offline strain (+ color)
- 6. Graag ook in A4C licht uitgedraaid LA beeld met nauwe sector width (voor offline LA strain)
- 7. Graag RV modified view nauwe sector width
- 8. Graag 3D TTE-beeld (bij voorkeur 4 loop beat, zo belangrijke stitching high volume rate)
- 9. Graag 3D-beeld RV (bij voorkeur 4 loop beat, zo belangrijke stitching high volume rate)
- 10. Subcostaal (met VCI view)
- 11. Pulsed wave at opening MV leaflets
- 12. Pulsed wave pulmonaal vene
- 13. TDI septale mitraal annnulus
- 14. TDI laterale mitraal annulus
- 15. Pulsed wave LVOT
- 16. Continuous wave AV
- 17. TAPSE RV
- 18. TDI met PW op Tricuspiedannulus (voor RV S')
- 19. So moderate to servere MI : downshift baseline voor offline PISA
- 20. RVSP

Er moeten geen online metingen uitgevoerd worden.

Measurements will be performed by a specialized nurse or the researcher. The parameters will be analyzed by the researcher to minimize inter-observer variability. The following echocardiographic parameters will be ascertained: left ventricle mass index (LVMI = LVM/m^2), left ventricular hypertrophy (LVH), relative wall thickness (RWT), left ventricle ejection fraction (LVEF), left ventricle geometry, and diastolic dysfunction.^{12,17}

LVM will be calculated via the area-length method [specific gravity and LV muscle volume (epicardial volume minus chamber volume, or endocardial volume)]:

LVM (g) =
$$\rho \left[\frac{5}{6}A_1(L+t) - \left(\frac{5}{6}A_2L\right)\right]$$

ho = specific gravity of muscle = 1.05g/mL A_1 = epicardial area at end diastole (cm²) A_2 = endocardial area at end diastole (cm²) L = ventricle length at end diastole (cm) t = average wall thickness (cm) LVH will be defined according to the Cornell Criteria: normal (0.50g/m² for man, 0.47 g/m² for women).

RWT is calculated as: $\frac{IVS+PWT}{IVS+PWT+EDD}$; 0.45 is the cutoff point.

IVS = interventricular septum thickness PWT = posterior wall thickness EDD = end diastolic diameter of the left ventricle

LVEF will be calculated using diastolic and systolic LV volumes measured by the single-plane Simpson's

rule method: ((Dvol - Svol)/Dvol) x 100; 0.50 is the cutoff point.

LV geometry is divided into four categories, based on LVMI and RWT:

[figure not shown]

Figure 5 Left ventricle classification system of Koren et al., adapted from Middleton et al.¹⁷

Diastolic dysfunction is defined as an abnormality of diastolic distensibility, filling, or relaxation of the left ventricle, regardless of whether the ejection fraction is normal or abnormal and whether the patient is symptomatic or asymptomatic.⁴⁶

4. Withdrawal of individual subjects

Participants can exit the study at any time for any reason if they wish to do so. The investigator can decide to withdraw a subject from the study for urgent medical reasons. In case of withdrawal, an end of study visit will be scheduled to perform last measurements according to visit 5. As there is no medication intervention in this study, there is no need for a safety procedure during withdrawal. Withdrawals will not be further followed.

5. Replacement of subjects withdrawn from treatment

Patients who withdraw from the study will not be replaced, as this has already been taken into account in the sample size calculation.

6. Premature termination of the study

As the interventions in this study are non-invasive and no medication is used, no specific termination criteria are formulated.

SAFETY REPORTING

1. Temporary halt for reasons of subject safety

The sponsor will suspend the study if there is sufficient ground that continuation of the study will jeopardize subject health or safety. The sponsor will notify the accredited Ethical Committee without undue delay of a temporary halt including the reason for such an action. The study will be suspended pending a further positive decision by the accredited Ethical Committee. The investigator will take care that all subjects are kept informed.

2. Adverse and serious adverse events, SUSARs

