- Central volume status, measured by thoracic BIS, photoplethysmography and echocardiography
- Blood pressure, measured by automatic oscillometric device
- Determinants of BIS signal in CKD population: gender, comorbidities
- Rate of kidney function decline, determined by eGFR CKD-EPI, mixed urea and creatinine clearance, and urine volume measured by 24h urine collection

Nature and extent of the burden and risks associated with participation, benefit and group relatedness:

- BIS and blood pressure measurements will be achieved by non-invasive techniques which pose a minimal burden to the patient.
- Blood sampling will as much as possible coincide with regular blood samplings for clinical purposes. The risk of venipuncture-related complications is considered moderate when performed in the non-dominant arm, as this can influence negatively on a future vascular access.
- All subjects undergo echocardiography. Analysis of the echocardiography will be done during follow-up period. Aberrant results will be discussed with an expert.
- All study-related costs will not be charged to the patient.

INTRODUCTION AND RATIONALE

Chronic kidney disease (CKD) is defined as abnormalities of kidney structure or function, present for more than 3 months, with implications for health.¹ Classification of CKD is structured according to the estimated glomerular filtration rate of creatinine (eGFR) and albuminuria (Figure 1). CKD is a major health problem and continues to rise globally. Prevalence of CKD is estimated at 11-13% of the adult population, of which 0.1% results in end stage renal disease (ESRD, defined as eGFR < 15ml/min or the need for renal replacement therapy).^{2,3} As well in developed as in developing countries, aging and the higher rate of cardiovascular (CV) events in the general population explains the increase of CKD.² Not only prevalence, but also mortality in CKD population is mainly determined by CV comorbidities.^{4,5} Besides the Framingham classics, novel CV risk factors such as fluid status (FS), malnutrition, inflammation and impaired kidney function itself have gained importance.^{4,6,7}

| | | | Persistent albuminuria categories Description and range | | | | | |
|--|--------|---|--|-----------------------------|--------------------------|--|--|--|
| | | | A1 | A2 | A3 | | | |
| | d Albu | sis of CKD by GFR uminuria Categories: KDIGO 2012 | Normal to mildly increased | Moderately increased | Severely increased | | | |

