1.1 Demographic and clinical data

The prevalent CKD stage 3 – 5 population will be screened by the researcher. After verification of the in- and exclusion criteria, eligible patients will be invited to participate the HORUZ study, with approval of their treating nephrologist. After signing the informed consent, data at baseline and during followup visits will be collected on paper clinical report forms (Table 1). Hypertension is defined as an office BP \geq 140/90 mmHg or home BP \geq 130/80 mmHg, or current medication for hypertension.¹ Diabetes mellitus will be assumed to be present in patients who report use of insulin and/or oral hypoglycemic agents. CV diseases include coronary artery disease, as documented by coronary angiography or a history of myocardial infarction, congestive heart failure, cerebrovascular accident, or known peripheral vascular disease. Fluid assessments, including BIS measurements, will be recorded on the HORUZ registration form (Appendix).

The healthy controls included for the cross-sectional analysis will only be followed according to visit 0 and 1.

| | Baseline Visit 0 | Month 1 Visit 1 | Month 3 Visit 2 | Month 6 Visit 3 | Month 9 Visit 4 | Month 12/ end of study Visit 5 |
|--|---------------------|--------------------|--------------------|--------------------|--------------------|-----------------------------------|
| Consent | х | | | | | |
| Demographics: Age (y) Gender Height (cm) Smoking status Etiology CKD Hypertension Diabetes CV disease Tx list | x | | | | | |
| eGFR _{creat} | x | x | x | x | x | x |
| CrUrCl | | x | x | x | x | x |
| 24h urine | | x | x | x | x | x |

Table 1 Schedule of the main data to collect in CKD subjects.

| BP | x | | x | x | x | x |
|-----------------|---|---|---|---|---|---|
| ECG | x | | x | x | x | x |
| Echo cor | | x | | | | x |
| CV events | | x | x | x | x | x |
| Hospitalization | | x | x | x | x | x |
| Medication | x | | x | x | x | x |
| Whole body BIS | x | | x | x | x | x |
| Thoracic BIS | x | | x | x | x | x |
| SF36 | x | | | | | x |
| Adverse event | | x | x | x | x | x |

Abbreviations: BIS, bioimpedance spectroscopy; BP, blood pressure; CKD, chronic kidney failure; Creat, creatinine; CrUrCl, mixed creatinine

and urea clearance; CV, cardiovascular; ECG, electrocardiography; M, month; SF36, short form 36 questionnaire; Tx, transplantation.

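### No masking is specified for the offline echocardiographic reading, so a single reader limits inter-observer variability but not expectation bias in the secondary cardiac outcomes (minor, cheap to improve)

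*Combined protocol and SAP*

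**What the plan says.** Methods, section 3.3, has professional echocardiographists acquire the images to a standard list of views. The Dutch instruction closing that list, "Er moeten geen online metingen uitgevoerd worden", means that nothing has to be measured at acquisition. The section continues: "Measurements will be performed by a specialized nurse or the researcher". Then: "The parameters will be analyzed by the researcher to minimize inter-observer variability". That is the only safeguard given for the reading.

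On timing, section 3.3 states: "At baseline and end of the study, an echocardiography will be planned to evaluate cardiac function". The Summary and section 4 of the Ethical Considerations both add: "Analysis of the echocardiography will be done during follow-up period". Both also provide for aberrant findings to be discussed with an expert.

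The researcher's title appears elsewhere in Methods. Section 1.1: "The prevalent CKD stage 3 – 5 population will be screened by the researcher". Section 3.1: "The researcher will evaluate the BP each study visit". The registration form in the Appendix has one row per visit. Its columns cover visit number, thoracic and whole-body BIS (including overhydration), ECG and echocardiography, and kidney function.

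Neither Methods nor Statistical Analysis mentions masking, coded images, reading order or repeat reading.

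**The concern.** Having one reader deals with one source of error, differences between readers. It leaves a second untouched: a reader who knows whether a scan belongs to a fluid-overloaded patient, a stage 5 patient or a healthy control may resolve borderline borders and frames in the expected direction. That error is systematic, so it does not shrink as the sample grows.

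The protocol gives the reader a direction to expect. The Introduction presents hypervolemia and hypertension as drivers of left ventricular hypertrophy, and the Hypothesis section expects the thoracic BIS signal to match echocardiography as a predictor of cardiac function. At stake are the secondary comparisons of systolic and diastolic function and central volume status, and any statement about how well thoracic BIS tracks echocardiography. A reader aware of the BIS value could make the two methods appear to agree better than they do.

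**Working it through.** **Step 1. Could the reader know the group?** The protocol gives screening, blood-pressure review at each visit and echocardiographic analysis to the same title. Reading takes place while BIS and eGFR data are accruing, and the form shows these on the same row as the echocardiography column. Nothing in the text separates the reader from this information.

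**Step 2. Do the measures leave room for judgement?** Section 3.3 derives LV mass from epicardial and endocardial areas, ventricle length and wall thickness, and LVEF from single-plane volumes. Relative wall thickness is cut at 0.45 and LVEF at 0.50, so a small shift can move a patient across a threshold. Diastolic dysfunction is defined in words, without numerical criteria.

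**Step 3. Would the planned analysis detect or remove a shift?** Statistical Analysis plans chi-squared tests, t-tests and regression for secondary parameters, and adjusts LVH for systolic blood pressure and haemoglobin. None of these addresses reader bias.

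**Step 4. Is the primary endpoint affected?** No. Section 1.2 has eGFR calculated uniformly in the laboratory.

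**Step 5. The only group size in the plan.** The sample size section uses a difference of 2 and an SD of 4.7 per year, alpha 0.05 and power 0.8. Two-sided:

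n = 2 × [4.7 × (1.960 + 0.842) / 2]² = 86.7 per group

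This reproduces the stated 86 to within rounding. It belongs to the eGFR comparison of fluid-overloaded with other patients. No size is given for any echocardiographic comparison.

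**Step 6. Illustration of what a shift would do.** Assume no true difference, a reader shift of b SD between two groups of n, and a two-sided 5% test:

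false-positive rate = 1 − Φ(1.96 − b/√(2/n)) + Φ(−1.96 − b/√(2/n))

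For n = 86, √(2/86) = 0.1525. For n = 103 (the plan's figure after drop-out allowance), √(2/103) = 0.1394.

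| Assumed shift b | b/√(2/86) | Rate, n = 86 | Rate, n = 103 |
|---|---|---|---|
| 0 | 0 | 5% | 5% |
| 0.1 SD | 0.66 | 10% | 11% |
| 0.2 SD | 1.31 | 26% | 30% |
| 0.3 SD | 1.97 | 50% | 58% |

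The larger group has the higher rate, as expected for an error that does not average out. The values of b are assumptions; the documents give no echocardiographic SD and no estimate of reader bias.

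**The case against.** **Silence is not unmasked reading.** A reader might infer that the scans will be read with full knowledge of group. The documents do not say so. They specify no masking, and the study team may already work from coded files. This stands and limits the claim to what the plan leaves open.

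**Who measures, and how, is unclear.** It is tempting to picture one person who screens, measures and traces every border by hand. Section 3.3 does not say whether tracing is manual, semi-automated or automated. Its sentence naming a nurse or the researcher may refer to the offline measurements, in which case the researcher might only derive parameters from a nurse's readings. This stands too. It does not remove the point, because no masking is specified for either person.

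**The percentages are not tied to a planned comparison.** A reader might take 26% or 50% as the error rate of the cardiac analyses. That is not supported. Section 1.3 compares cardiac outcomes between CKD stages, and the Objectives add healthy controls; a comparison by fluid overload could be inferred from the secondary objective but is not specified for echocardiography. An equal split of 206 patients over three stages would be about 69 each (206/3), but neither stage sizes nor the number of controls is given. The figures also say nothing about agreement between echocardiography and thoracic BIS, for which Statistical Analysis has no dedicated method.

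**Full masking to visit would conflict with the plan.** Mixing a patient's two scans in random order means holding the first until month 12. Across the whole cohort the wait could approach 30 months (18 of inclusion plus 12 of follow-up). The plan places analysis, and the discussion of aberrant findings, within follow-up, and offline reading is the only reading described. This stands, so the remedy must not defer reading.

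**Echocardiography is secondary in a non-randomised, largely descriptive study.** This lowers the severity. It does not make the reading less open to bias.

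**Conclusion.** The point holds as a minor one. Section 3.3 assigns the echocardiographic analysis to the researcher, offline, with a single reader as the only safeguard, and no masking is specified. That safeguard does not address expectation bias in the secondary cardiac outcomes or in the comparison with thoracic BIS. The primary eGFR endpoint, the sample size, alpha and power are unaffected.

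The size of any bias is unknown. The 10%, 26% and 50% figures show only how sensitive a two-group test would be to an assumed shift of 0.1, 0.2 or 0.3 SD at 86 per group. They are not evidence that a shift exists. The conclusion rests on the absence of any masking provision and on the shared title; if the title covers several people, or coded reading is already practised, the remaining gap is that the protocol does not record it.

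**What to change.** Add two or three sentences to section 3.3:

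- Existing staff other than the reader code each image file as it arrives, removing name, CKD stage, case/control status and BIS result, and the visit label where feasible. Visit masking will be incomplete, because early batches will consist mainly of first scans.
- The same researcher, and the nurse if the nurse does the measuring, reads the coded files in batches during follow-up, without waiting for the month-12 scan.
- Readings are locked before they are linked to BIS, fluid status and eGFR data.
- Someone other than the reader holds the re-identification key, so that aberrant results still reach the expert already foreseen.

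The same passage should state who performs the offline measurements.

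The cost is file coding and custody of the key. The documents give no cost figures, so calling it small is a judgement. It rests on acquisition and reading already being separate and on study numbers already being on the form. No extra reader, visit or patient is needed, and the single-reader rationale is kept.

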1.3 Secondary endpoints

The secondary objective is to identify the clinical factors associated with FO during a longitudinal follow up. Secondary outcomes of interest are the central volume status (measured by echocardiography and thoracic BIS in combination with photoplethysmography), BP, the cardiac systolic and diastolic function, CV events, hospitalizations, inflammatory- and nutrition status, and quality of life, between CKD stages 3, 4 and 5.

- 1. *Cardiac function:* Electrocardiography and echocardiography (see point 3.3) will be scheduled at baseline, and at 12 months or at end of study visit.
- Thoracic BIS values: a wearable device from Imec Eindhoven will be used to measure thoracic
 BIS values in combination with photoplethysmography and cardiopulmonary index.
- 3. *Blood pressure:* patients will be asked to take BP measurements at home three times a week twice daily with an automatic BP monitor. Mean arterial pressure corrected for heart

frequency will be calculated. BP measurements can be transmitted to the researcher by use of the local Dharma platform.

- 4. *CV events:* CV events defined as hospitalization for coronary disease, heart failure, stroke or peripheral artery disease will be recorded during follow-up.
- 5. *Hospitalization rate and indication:* hospitalization rate and indication will be listed.
- 6. *Inflammatory- and nutrition status:* CRP, ferritin and albumin will be determined every visit (Table 2). Fat tissue mass and lean tissue mass will be analyzed by BIS measurements.
- 7. *Quality of Life assessment:* SF36 questionnaire will be filled in at baseline and end of study visit.

| Table 2 Overview of | f parameters evaluatir | g kidney function, r | enal metabolism a | and inflammation in HORUZ study. |
|---------------------|------------------------|----------------------|-------------------|----------------------------------|

| Assay | Material | Standard care | Frequency |
|-------------------------|--------------|---------------|-------------------|
| Residual renal function | | | |
| Urea | Plasma/serum | yes | Every study visit |
| Creatinine | | | |
| Metabolism and electrol | ytes | | |
| Hemoglobin | Plasma/serum | yes | Every study visit |
| Sodium | | | |
| Potassium | | | |
| Bicarbonate | | | |
| Phosphate | | | |
| Calcium | | | |
| NT-proBNP | | No | Every study visit |
| Inflammation | | | |
| C-reactive protein | Plasma/serum | yes | Every study visit |
| Leucocytes | | | |
| Albumin | | | |

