2.3 Suspected unexpected serious adverse reactions (SUSAR)

Not applicable.

3. Follow-up of adverse events

AE according to the study are considered very unlikely, due to the fact that only non-invasive methods are used. All AEs will be followed until a stable situation has been reached and treated to standard procedures.

4. Data Safety Monitoring Board (DSMB)

Not applicable.

STATISTICAL ANALYSIS

A table with baseline characteristics of all subjects will be provided. Baseline characteristics of the population will be expressed as the mean \pm standard deviation if normally distributed, or as the median [25th – 75th percentile] as not normally distributed, for continuous and dichotomous data, and as the frequency (%) for categorical data. Measurements of drop-outs will be included until the moment of withdrawal from the study. Normality in distribution will be tested by the Shapiro-Wilk statistic. Repeated measurements ANOVA techniques will be used for analysis. Pearson's Chi-squared test will be used to assess whether there is any distinction between subgroups in rate of kidney function decline. In case the analysis of the baseline characteristics showed any clinically relevant imbalance, we will also perform a multivariable logistic regression analysis in order to correct for this imbalance. Differences in LVH will be corrected for systolic BP and haemoglobin, as these are predictors of LVH in predialysis population.¹⁵ Depending on the level of measurement a Chi-squared test or a T-test will be used to assess differences in secondary study parameters, and logistic and linear regression for baseline-corrected estimates. Tests will be considered significant if p-values are ≤ 0.05 .

ETHICAL CONSIDERATIONS

1. Regulation statement

The study will be conducted according to the principles of the Declaration of Helsinki (Fortaleza, Brasil, 2013).

2. Recruitment and consent

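### LVEF is computed in percent but cut at 0.50 with no direction stated, and from one unnamed plane although both apical views are already recorded

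*Combined protocol and SAP*

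**What the plan says.** Section 3.3 (Cardiac function) gives the volume method as follows: "LVEF will be calculated using diastolic and systolic LV volumes measured by the single-plane Simpson's", continuing "rule method: ((Dvol - Svol)/Dvol) x 100; 0.50 is the cutoff point". No plane is named, the threshold carries no unit, and no direction is given.

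The acquisition list in the same section includes item 3, "Apicale 4 kamer (A4C) window + idem met nauwe sector width voor offline strain (+ color", and item 4, "Apicale 2 kamer (A2C) window + idem met nauwe sector width voor offline strain (+ color". It adds that no online measurements are needed, so tracing is done afterwards, and the researcher analyses the parameters. LVEF is one of six parameters to be ascertained; the list ends with "left ventricle ejection fraction (LVEF), left ventricle geometry, and diastolic dysfunction".

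Section 1.3 (Secondary endpoints) names as outcomes "the cardiac systolic and diastolic function, CV events, hospitalizations, inflammatory- and nutrition status, and quality of life, between CKD stages 3, 4 and 5". For these, the Statistical Analysis section says "Depending on the level of measurement a Chi-squared test or a T-test will be used to assess differences in secondary study parameters". It does not say whether LVEF is treated as a continuous value or as a category.

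**The concern.** There are two weaknesses in one definition.

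- **Scale.** A percentage is compared with a fraction. Someone who programs the sentence as printed gets a classification that separates nobody.
- **Plane.** A single-plane volume extrapolates the whole ventricle from one cut, so it cannot see a wall-motion defect in walls outside that cut. The plane is chosen offline and is not fixed in the text. It could therefore differ between patients, or between the two echocardiograms of one patient, and method variation would then enter both the group comparisons and the change over time.

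The second weakness matters because the exclusion criteria remove only acute cardiovascular events in the 3 months before screening. Section 1.1 records coronary disease, past infarction and heart failure as baseline conditions, so patients in whom the two planes may disagree can enter. LVEF is also the only systolic measure among the six listed echo parameters, so it carries the systolic part of the secondary outcome.

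**Working it through.** **Inputs from the protocol (section 3.3).** LVEF = ((Dvol − Svol)/Dvol) × 100; threshold 0.50; single-plane volumes; A4C and A2C both acquired.

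**1. The threshold as printed.** A value falls below 0.50 only if (Dvol − Svol)/Dvol < 0.005, that is, if Svol > 0.995 × Dvol. Example volumes (assumed, in mL):

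| Dvol | Svol | LVEF by formula | Below 0.50 as printed? | Below 50? |
|---|---|---|---|---|
| 100 | 45 | 55 | no | no |
| 100 | 50 | 50 | no | no |
| 100 | 55 | 45 | no | yes |
| 150 | 120 | 20 | no | yes |
| 200 | 180 | 10 | no | yes |
| 200 | 199.1 | 0.45 | yes | yes |

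Dropping the × 100 and keeping 0.50 gives the same answers as the last column. Either consistent scale works; only the mixture fails.

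**2. The size of the mismatch in a population.** The documents give no LVEF distribution, so normal distributions are assumed here.

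- Mean 45, SD 10: (50 − 45)/10 = 0.5, so about 69% lie below 50.
- Mean 55, SD 10: (50 − 55)/10 = −0.5, so about 31%.
- Mean 60, SD 8: (50 − 60)/8 = −1.25, so about 11%.
- Against 0.50 the nearest case is (0.5 − 45)/10 = −4.45, so effectively 0% in all three.

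**3. Dependence on the plane traced.** The volumes below are assumed for one heart and chosen to show that the answer can change.

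- A4C 120/54 mL: (120 − 54)/120 = 55%, not below 50.
- A2C 120/72 mL: (120 − 72)/120 = 40%, below 50.
- Both planes, with volumes simply summed as an approximation to biplane: (240 − 126)/240 = 47.5%, below 50.

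The planned rule allows 55% or 40% for this heart, according to the view chosen. This shows that disagreement is possible. It does not estimate how often it occurs.

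**4. What is not touched.** The primary endpoint is the eGFR slope. The sample size uses a difference of 2 and an SD of 4.7 in eGFR decline. LVEF enters neither.

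**The case against.** The strongest reply on scale is that no competent analyst would read an ejection-fraction threshold of 0.50 as half of one percent. The threshold for relative wall thickness just before it, 0.45, is also written as a fraction, there for a ratio without the × 100. If the text were coded literally, a result with nobody below the line would be noticed at once. This stands. A reader might infer from the printed rule that systolic dysfunction will be misclassified, or that no abnormal cases will be found. The documents do not support that: 50% is the evident intention, and they announce no analysis of LVEF as a dichotomy. If LVEF is compared as a continuous value by t-test, the threshold plays no part.

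The reply on planes is that single-plane is a stated method and that preferring biplane is a choice. The documents contain no single-plane error figure, no comparison of methods and no prevalence of regional wall-motion defects. The echo parameters also cite sources that may explain the choice. This stands against any claim of known error or of bias between CKD patients and healthy controls. It does not answer two points that need no outside source: the plane is unnamed, and one cut cannot show what lies outside it.

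A reader might also take LVEF to be the reference standard for the thoracic bioimpedance hypothesis. The Hypothesis section compares the signal with echocardiography for cardiac function in general and does not name LVEF.

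Finally, a rule that falls back to one plane when a view is poor can mix methods within and between patients. That objection is fair, and the fix has to deal with it.

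**Conclusion.** The threshold is wrong as written, by a factor of 100 and without a direction. This is minor because the intended value is plain. The single-plane rule is under-specified, and a better method is available from images the study already collects; that part is a cheap improvement rather than the correction of a demonstrated error. LVEF could depend on the view traced and could miss regional dysfunction outside it. Neither the frequency nor the effect on any comparison can be sized from the documents. The 55%, 40% and 47.5% in the working rest on assumed volumes, and the 11% to 69% on assumed distributions.

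The consequence is confined to a secondary parameter. The geometric point assumes only that some enrolled patients have wall-motion defects confined to part of the ventricle, which the eligibility criteria permit.

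**What to change.** Replace the LVEF sentence in section 3.3 with a definition that contains the following:

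- LVEF = ((Dvol − Svol)/Dvol) × 100, in percent; cutoff 50%, with values below 50% classed as reduced.
- Volumes by the biplane Simpson's rule from the A4C and A2C views (items 3 and 4 of the acquisition list).
- If A2C cannot be traced at one or both of a patient's echocardiograms, use A4C single-plane at both for the within-patient change, and flag the patient. For a comparison at one time point, use biplane where it exists and flag the single-plane values.
- As a sensitivity analysis, repeat the comparisons with A4C single-plane in everyone. Biplane already requires the A4C tracing, so this adds no measurement.

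In the Statistical Analysis section, say whether LVEF is compared as a continuous value, as a category, or both.

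The cost is protocol wording and a few extra minutes of offline tracing per echocardiogram by the same researcher. With two echocardiograms per CKD patient in Table 1, that is at most 206 × 2 = 412, plus those of the controls. No new images or visits are needed. The drawback is that some A2C views will be untraceable, so a flagged subset will remain on one plane.
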